The registry is approved by the Norwegian General Data Protection Regulation (16/00482-11/CDG), the South East Norway Health Authority Ethical Committee (2016/588), and the Data Protection Officers at Oslo University Hospital (2016/924) and Diakonhjemmet Hospital (7/12–2019). The NCRR comprises routinely recorded administrative data, and written consent from study subjects was not required.

For this study, we will use data from three key sources: The Norwegian Prescription Registry (NPD) serves as the foundation for prescription data, The Norwegian Patient Registry (NPR) provides diagnosis data, and data regarding age and sex are extracted from Statistics Norway (SSB). The data from these registers provide accuracy up to the month and year, but not to the exact date of events, like prescriptions or diagnoses.

5. Data preparation and eligible treatment periods in the target trial emulation

To maintain comparability between the methylprednisolone and prednisolone treatment groups in the emulated study, we will apply several data management steps:

- 1) Individuals aged \leq 18 years in January 2008 will be excluded
- 2) Analyses will be restricted to tablets, as prednisolone is only available in this form.
- 3) To allow for equipotent dose comparisons, we will focus only on 4 mg and 16 mg methylprednisolone and their counterparts in prednisolone at 5 mg and 20 mg, respectively. Patients with other doses will be excluded.
- 4) To facilitate comparisons of treatments prescribed for similar conditions, we will only include prescriptions with an International Classification of Diseases, 10th Edition (ICD10) or International Classification of Primary Care, 2nd Edition (ICPC2) refund code.
- 5) Patients with prescriptions for diagnosis codes including palliative care, cancer symptoms, medical complications, and organ transplants will be excluded. This exclusion aims to reduce the inherent heterogeneity within these groups, allowing for a more comparable baseline risk.
- 6) An initial 2-year observational period, spanning from January 2008 to December 2009, will be used to establish comorbidities. Accordingly, only prescriptions of methylprednisolone or prednisolone dispensed from January 2010, onward, will be eligible for analyses.

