- 7) To minimize the risk of carry-over effects, we will exclude all prescriptions prescribed \leq 6 months after another prescription for a corticosteroid. Accordingly, the same patient can contribute data on several treatment courses, provided that there was $>$ 6 months since the last prescription was dispensed (See section 7 for justification for why a 6-month interval was chosen).
- 8) Duplicate prescriptions (same date, drug and dosage) will be kept in the analyses as a single treatment course. Cases of duplicate prescriptions on the same date, but where the drug or dosage is different will be excluded.

9) Baseline of the treatment course will be defined as the date when the prescription of either methylprednisolone or prednisolone was dispensed.

6. Emulated target trial matching procedure

In order to create balanced treatment groups and reduce the potential for confounding in the emulated study, we will apply a matching process for baseline characteristics including relevant comorbidities. Each methylprednisolone treatment course will be matched 1:1 with a prednisolone treatment course. The following characteristics will be matched for:

- Sex
- Age groups, defined as: < 45 years; 45 up to < 60 years; 60 up to < 75 years; 75 years or higher
- Equipotent dosage (4 mg methylprednisolone versus 5 mg prednisolone; 16 mg methylprednisolone versus 20 mg prednisolone). While prescription data from the NPD cannot provide the exact number of tablets of either medicine taken per day, we will assume that since the medications are taken by comparable populations and for comparable conditions, any differences will even out in this large dataset.
- Prescription groups based on ICD10 / ICPC2 refund codes:
 - i. Pulmonary
 - ii. Rheumatology and musculoskeletal
 - iii. Neurology and ophthalmology
 - iv. Dermatology
 - v. Endocrinology and metabolic
 - vi. Gastrointestinal
 - vii. Hematology and immunology
 - viii. Nephrology.
- Comorbidities as categorical variables (a. – e. defined as at least one ICD10 diagnosis code from a secondary or tertiary healthcare provider or at least one prescription of medication with relevant ICPC2 or ICD10 refund codes)
 - a. Atherosclerotic cardiovascular disease (coronary, cerebral and peripheral artery disease)
 - b. Chronic kidney disease
 - c. Diabetes (type 1 and 2)
 - d. Hypertension
 - e. Heart failure

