Second, for the purpose of matching methylprednisolone and prednisolone prescriptions, we have categorized them into broad disease groups based on ICD10/ICPC2 refund codes. While this approach is necessary due to the nature of the available data, it introduces a level of generalization that might overlook nuances in patient diagnoses. The broad categorization may not perfectly align the severity or specific characteristics of the conditions being treated, which could affect the comparability between the two treatment groups.

Third, our data includes information about comorbidities, but lacks details regarding the severity of these conditions. This gap means we cannot fully account for the potential

impact of the severity of comorbidities on the outcomes of interest. It is plausible that more severe comorbid conditions could influence the choice of medication or affect the risk of heart failure decompensation independently of the corticosteroid used.

Fourth, in clinical practice, the choice between methylprednisolone and prednisolone might be influenced by the treating physician's perception of their relative efficacy, particularly in patients with heart failure. This selection bias could mean that methylprednisolone is preferentially prescribed to patients perceived to be at higher risk of heart failure decompensation, based on the hypothesis that it might be better. By calculating the E-value the reader will be able to evaluate themselves whether the likelihood that the observed differences were due to unmeasured confounding. Should the E-value be large, this would suggest that considerable unmeasured confounding would be required to negate the observed effect. Conversely, a small E-value would indicate that our results could be more susceptible to bias from unmeasured confounding. The E-value thus complements our 1:1 matching process and provides additional context for interpreting the possible impact of unmeasured variables on our study outcomes.

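### Age is matched only in four wide bands and indication only in eight organ-system groups, and no later adjustment is specified, although age and a refund code are held for every course

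*SAP*

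**What the plan says.** Section 6 sets the ratio: "Each methylprednisolone treatment course will be matched 1:1 with a prednisolone treatment course". Age enters as "Age groups, defined as: < 45 years; 45 up to < 60 years; 60 up to < 75 years; 75 years or higher". Indication enters as "Prescription groups based on ICD10 / ICPC2 refund codes", collapsed to eight organ systems. The other matching factors are sex, equipotent tablet strength and seven comorbidity or medication indicators.

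Finer information on both variables is held. Under Section 4, age comes from Statistics Norway. Under Section 5, item 4, a prescription is eligible only if it carries an ICD10 code "or International Classification of Primary Care, 2nd Edition (ICPC2) refund code". Item 5 then works below organ-system level: "Patients with prescriptions for diagnosis codes including palliative care, cancer symptoms, medical complications, and organ transplants will be excluded". Section 11 lists age and refund codes among the characteristics to be summarised in Table 1.

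For the outcomes, Section 11 leaves the method to be chosen later with regard to the matched design, and names no covariates. It adds an E-value for unmeasured or residual confounding. Section 12 discloses the loss of diagnostic detail and gives this reason for the disease groups: "While this approach is necessary due to the nature of the available data, it introduces a level of generalization". It does not mention the age bands.

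**The concern.** Exact matching on a coarse category balances the category, not the variable beneath it. Two courses in the same cell can differ by up to 15 years of age in the middle bands, and by more in the outer two. They can also be for diseases with different courses and different background risks of fluid retention, loop diuretic use or heart failure. If prescribers favour one drug for older patients in a band, or for particular diagnoses in a group, the comparison picks that up as a drug effect.

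Section 12 closes by arguing that a result favouring methylprednisolone would run against the expected bias and so be noteworthy. That argument considers only selection of higher-risk patients to methylprednisolone. An age or diagnosis difference inside cells could run either way, including towards the hypothesised benefit.

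**Working it through.** The SAP gives no sample size, event count or imbalance data, so there is no figure of its own to reproduce. The check has three parts.

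**1. How coarse is the matching?**
- Two of the four age bands are 15 years wide, and the top band is open.
- The lowest band: people aged 18 or under in January 2008 are excluded and courses count from January 2010, so the youngest are about 19 + 2 = 21. The band then spans about 45 − 21 = 24 years.
- Cells: 2 sexes × 4 age bands × 2 strengths × 8 indication groups = 128. With seven binary indicators, 128 × 2^7 = 16,384.
- Section 6 does not say which prednisolone course is taken when a cell offers several, so age in years plays no part in the choice.

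**2. What could a within-band age difference do?** Assumptions, none from the SAP: heart failure risk rises by a factor r per decade, log-linearly, with r from 1.5 to 2.5; mean age differs between the drugs by d = 2 or 3 years within bands. Spurious risk ratio = r^(d/10).

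| r | d = 2 years | d = 3 years |
|---|---|---|
| 1.5 | 1.5^0.2 = 1.08 | 1.5^0.3 = 1.13 |
| 2.5 | 2.5^0.2 = 1.20 | 2.5^0.3 = 1.32 |

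If methylprednisolone users are the younger ones, the inverses apply: 1/1.084 = 0.92 to 1/1.316 = 0.76.

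A second parameterisation, 2^(d/D) with risk doubling every D = 7 to 15 years, gives for d = 1 to 3 years a range from 2^(1/15) = 1.05 to 2^(3/7) = 1.35. The order of size does not hinge on the form chosen. Neither calculation conditions on the matched comorbidities, which would absorb part of the age gradient.

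**3. What could a within-group diagnosis difference do?** Assumptions: one sub-indication in a group has R times the risk of the rest, with R from 1.5 to 3. It makes up 50% to 60% of one arm and 40% of the other. Spurious risk ratio = [1 + p1(R − 1)] / [1 + p2(R − 1)].
- Low end: (1 + 0.5 × 0.5) / (1 + 0.4 × 0.5) = 1.25/1.20 = 1.04.
- High end: (1 + 0.6 × 2) / (1 + 0.4 × 2) = 2.2/1.8 = 1.22.

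The inverses, 0.96 to 0.82, are equally possible. This effect could add to the age effect or offset it.

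**The case against.** The strongest reply is that the plan already does much of the work. Pairs agree on sex, tablet strength, indication group and seven indicators that include heart failure, hypertension, kidney disease and atherosclerotic disease. COPD is matched separately, which refines the pulmonary group. Section 12 openly admits that the disease groups lose detail. Table 1 could reveal an imbalance if it is shown by matched arm. Some grouping may also be sensible: there are two coding systems to reconcile, the scheme already has up to 16,384 cells, and the SAP does not say how specific the refund codes are.

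Most of this stands as a limit on size, and as a reason not to make exact-code matching the primary scheme. It does not answer the age point, where the remedy leaves the cells as they are. Nor does Table 1 repair anything, since the plan prescribes no response to an imbalance. The practical reasons for grouping are not the ones the SAP gives.

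A reader might infer three stronger points that the document does not support:
- That the SAP calls its age bands necessary. The sentence in Section 12 concerns the disease groups only; the age bands are simply unexplained.
- That the E-value is aimed at the wrong target. Section 11 offers it for residual as well as unmeasured confounding. It remains a description of sensitivity, and adjusting for a variable in hand is better, but its stated purpose is not wrong.
- That confounding is present. The SAP has no data on age or diagnosis mix by drug.

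**Conclusion.** The point holds as an improvement that the existing data allow. Age and a refund code are held for every included course, the matching uses only coarse versions of both, and Section 11 specifies nothing to recover the rest. Bias arises only if the drugs differ in age or diagnosis mix within matched cells. Its size and direction are unknown. The age illustration of 1.08 to 1.32, or 0.92 to 0.76, rests wholly on the assumed risk gradient and the assumed 2- to 3-year difference, and is likely an upper view because the comorbidity matching is ignored. It also takes age to be available in years, which the planned numerical summaries in Section 11 suggest but do not state. The indication effect cannot be sized from the SAP. The stated reason for the disease groups is not borne out by Section 5 as it stands.

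**What to change.** - **Section 6:** within each matching cell, select the prednisolone course nearest in age in years, with a stated rule for ties. Against any other one-to-one choice in the same cells this loses no pairs.
- **Section 11:** include continuous age in the outcome model, whichever method is finally named. This costs one covariate.
- **Section 11:** add a sensitivity analysis that matches on, or adjusts for, finer refund-code categories after mapping ICD10 and ICPC2 codes to common categories. Without that mapping, one disease coded in the two systems would count as two indications. The cost is the mapping work and, if matching is used, fewer pairs.
- **Section 12:** replace the statement that the grouping is forced by the data with the actual reason, such as reconciling two coding systems or avoiding sparse cells if that is the case, and list the age bands among the limitations.

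All of this is SAP wording and analysis code; no new data are needed.
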